3.4 Sample Size / Power

As there will be no formal hypothesis testing in this study, the sample size of 30 patients was based on practical, rather than statistical, considerations.

4 SCHEDULE OF STUDY PROCEDURES

The following data collection time table was abstracted from [Appendix 2](#) of the protocol, Schedule of Assessments:

Implant	Screening	1					2					3					4					Follow-Up [12]		
		0	14	30	60	90	0	14	30	60	90	0	14	30	60	90	0	14	30	60	90	0		
Day	Visit	1	2	3	4	5	6	7	8	9	10	11	12	13	14	15	16	17	18	19	20	21		
Informed Consent	X																							
PE / VS / Medical History	X	X	X	X	X	X	X	X	X	X	X	X	X	X	X	X	X	X	X	X	X	X		
ConMed / AE Review	X	X	X	X	X	X	X	X	X	X	X	X	X	X	X	X	X	X	X	X	X	X		
Global Clinical Assessment Questionnaire	X			X	X	X			X	X	X			X	X	X			X	X	X	X		
Activities of Daily Living Rating	X			X	X	X			X	X	X			X	X	X			X	X	X	X		
Symptoms Rating / Severity Assessment	X			X	X	X			X	X	X			X	X	X			X	X	X	X		
Quality of Life Scale	X			X	X	X			X	X	X			X	X	X			X	X	X	X		
Pain Scale Assessment	X		X	X	X	X		X	X	X	X		X	X	X			X	X	X	X	X		
ECOG Performance Scale	X			X	X	X			X	X	X			X	X	X			X	X	X	X		
Neurological Examination	X		X	X	X	X		X	X	X	X		X	X	X	X		X	X	X	X	X		
Phlebotomy	X		X	X	X	X		X	X	X	X		X	X	X	X		X	X	X	X	X		
12-Lead ECG	X					X					X					X								
Urinalysis	X					X					X					X								
Tumors Markers (CEA, CA19-9)	X		X	X	X	X		X	X	X	X		X	X	X	X		X	X	X	X	X		
CA125	X		X	X	X	X		X	X	X	X		X	X	X	X		X	X	X	X	X		
Hematology Profile [1]	X		X	X	X	X		X	X	X	X		X	X	X	X		X	X	X	X	X		
Coagulation Panel [2]	X		X	X	X	X		X	X	X	X		X	X	X	X		X	X	X	X	X		
Sedimentation Rate	X		X	X	X	X		X	X	X	X		X	X	X	X		X	X	X	X	X		
Comprehensive Metabolic Panel [3]	X		X	X	X	X		X	X	X	X		X	X	X	X		X	X	X	X	X		

Implant	Screening	1					2					3					4					Follow-Up [12]			
		Day		0	14	30	60	90	0	14	30	60	90	0	14	30	60	90	0	14	30	60	90		
		Visit		1	2	3	4	5	6	7	8	9	10	11	12	13	14	15	16	17	18	19	20	21	
GGT [4]	X			X	X	X	X	X		X	X	X	X		X	X	X		X	X	X	X	X		
Amylase [5]	X																								
Lipase [5]	X																								
Lactate Dehydrogenase	X			X	X	X	X	X		X	X	X	X		X	X	X		X	X	X	X	X		
C-Reactive Protein	X			X	X	X	X	X		X	X	X	X		X	X	X		X	X	X	X	X		
Bilirubin, Direct	X				X	X	X				X	X	X			X	X	X			X	X			
Hepatitis Panel [6]	X																								
HIV	X																								
Serum Pregnancy (Qualitative) [7]	X							X						X					X						
Immunoglobulin Levels [8]	X							X						X					X						
Cytokine Panel [9]	X			X	X	X	X	X		X	X	X	X		X	X	X		X	X	X	X	X		
Cellular Immune Function [10]	X							X						X					X						
Ecotropic Murine Leukemia Virus	X				X			X			X		X			X			X			X		X	
Immunohistochemical & Gene Array Analysis (when indicated)		X						X						X					X						
Murine Allergen Skin Test	X							X						X					X						
Positive and Negative Skin Test	X							X						X					X						
Circulating Tumor Cells	X			X			X			X			X			X			X			X			
Macrobuds Implantation (8 per kg body weight)		X						X						X					X						
Cefazolin (Prophylaxis – 1 gm)		X						X						X					X						
Chest X-Ray (PA / lateral)	X						X						X					X							

Implant	Screening	1					2					3					4					Follow-Up [12]	
		0	14	30	60	90	0	14	30	60	90	0	14	30	60	90	0	14	30	60	90	120	
Day	Visit	1	2	3	4	5	6	7	8	9	10	11	12	13	14	15	16	17	18	19	20	21	
CT Scan Chest (Non-Contrast) [11]	X																						
MRI of Abdomen [11]	X					X	X				X						X				X		X
MRI of Pelvis [11]	X					X	X				X						X				X		X
Tumor Mass Biopsy (where indicated)		X					X					X					X						
PET-CT Scan Whole Body	X						X				X						X				X		X [11]
Radionuclide Bone Scan [11]																							

1. Hematology Profile: WBC, RBC, hemoglobin, hematocrit, MCV, MCH, MCHC, RDW, platelets, automated differential WBC
2. Coagulation Panel: PT, PTT, INR
3. Comprehensive Metabolic Panel: CO₂, sodium, potassium, chloride, creatinine, BUN, calcium, total protein, albumin, total bilirubin, alkaline phosphatase, AST, ALT, glucose
4. GGT: gamma glutamyl-transpeptidase
5. Amylase and lipase are done at baseline, then as medically necessary for individual subjects
6. Hepatitis Panel: Hepatitis B, C and E
7. Serum pregnancy only for females of childbearing potential
8. Immunoglobulin Levels: IgA, IgG, IgE and IgM
9. Cytokine Panel: IL-6, TNF- α , TNF receptors p55, TNF receptors p75
10. Cellular Immune Function: T cells; B cells; antibodies to diphtheria, tetanus, mumps, rubella; quantitative IgG subclasses, NK cells count (CD16)
11. Only if clinically indicated.
12. Long-term follow-up will begin after the patient's EOS visit, and will continue for the duration of each subject's life, at 6-month intervals during the first 2 years of follow-up and then yearly thereafter. All examinations and treatment during this time will be guided by optimal patient care principles and the decisions of the physicians providing overall health care to the patient.

5 ANALYSIS POPULATIONS

All subjects who receive at least one implant will be included in all efficacy and safety evaluations and will be referred to as the Treated Population.

6 GENERAL DATA HANDLING / PRESENTATION CONSIDERATIONS

6.1 Listing, Table, and Figure Formats

- In general, listings, tables, and figures will include all subjects in the Treated Population.
- Listings will be ordered by cancer type, unique subject identifier, study day, visit date, and data collection time, if appropriate.
- Tables and figures will be ordered by cancer type and study day and will include summaries for both cancer types individually as well as for all subjects combined.
- The order of cancer type presentation in listing, tables, and figures will be colorectal, then pancreatic.
- Listings will include subject identification, subject initials, subject age and sex, cancer type, study day, date, and data collection time, as applicable.
- Unscheduled data, such as repeat laboratory tests, will be listed but will not be summarized or analyzed.
- Partial dates will be listed as recorded; i.e., there will be no imputation of partial dates for listings.
- Dates will be presented as ddmmmyy.
- Times will be presented as hh:mm (24-hour clock).
- Laboratory data will be presented in conventional units.
- Missing data will be represented on listings as either a hyphen (“-”) with a corresponding footnote (e.g., “unknown” or “not evaluated”), as “N/A” with the footnote “not applicable,” or another entry with an explanatory footnote, whichever is appropriate.
- Missing descriptive statistics or p-values will be output as a hyphen with an explanatory footnote.
- Each listing, table, and figure will be numbered using a decimal-point system for identifying related listings, tables, and figures.
- Each listing, table, and figure will be titled with the listing / table / figure number and a description of the presentation.
- Column headers will contain the unit of measurement, if applicable.
- In tables, column headers will contain the overall sample size of the group associated with the column. The overall sample size will include subjects with missing values for the data presented in the column. The number of subjects with available data for the column will be shown in the body of the table.
- Footnotes will appear at the bottom of each page of listings and tables.

- All listings, tables, and figures will be presented in the landscape orientation with 1-inch margins on all sides.
- In general, the main body of listings and tables will be 10 pt Times Roman font (or similar).
- Footnotes will be 8 pt Times Roman font (or similar).
- Headers will be 12 pt Times Roman font (or similar).and will contain the protocol number and the page number and total number of pages of the particular listing, table or figure.
- Footers will be 8 pt Times Roman font (or similar).and will contain the data source (listings) or listing source (tables and figures), data sets used, program name, run time, and page number and total number of pages of the entire output file (e.g., the listings file).
- All listings, tables, and figures will be presented in black and white.
- Listings and tables will be produced by SAS® version 9.1.3 or higher (SAS Institute, Inc., Cary, NC).
- Figures will be produced by SAS® version 9.1.3 or higher, Microsoft® Excel version 2007 or higher (Microsoft Corp., Redmond, WA).

6.2 Data Analysis

- All analyses will be done using SAS® version 9.1.3 or higher.
- All analyses will be exploratory. No confirmatory statistical testing will be done.
- Categorical variables will be summarized as frequencies and percentages in each category. In general, continuous variables will be summarized by numbers of patients, means, standard deviations, medians and ranges. The number of decimal places for minimums and maximums will be the same as the original data. The number of decimal places for means, medians and interquartile ranges will be the same as the original data plus one. The number of decimal places for measures of variance will be the same as the original data plus two.
- Laboratory data with qualifiers (e.g., "<") will be listed with but summarized without the qualifier.
- All p-values will be presented as illustrated below:

p-value	Presentation
≥ 0.01	2 decimal places
< 0.01 but ≥ 0.001	3 decimal places
< 0.001 but ≥ 0.0001	4 decimal places
< 0.0001	< 0.0001

- All analyses will be exploratory and, as such, there will be no significance level adjustments to control type I error.
- All statistical tests will be two-sided.
- Unscheduled data will not be summarized or analyzed (but will be listed, as noted above).

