4 INVESTIGATIONAL PLAN

4.1 *Description of Overall Study Design and Plan*

This is an open-label clinical trial. The clinical trial will have duration of approximately 12 months and involve a potential total of four macrobead implants, each no less than three months apart.

Each subject will serve as his own control. This means that changes from baseline to various post-treatment time points will be analyzed for some variables (such as tumor markers, for example). The confidence intervals for these changes will be calculated. Of course, it is not planned for the survival analysis.

Seventy-four (74) male and female subjects with advanced pancreatic cancer or metastatic, treatment-resistant colorectal cancer meeting all the above inclusion criteria will be recruited and treated for the study. Baseline measurements will include tumor burden and size, tumor history and pathological diagnosis and grade, global clinical state, activities of daily living, symptom checklist including tumor-related symptoms, a sense-of-well-being scale, routine clinical biochemistry and any appropriate tumor markers as available, and an assessment of cellular and humoral immune status.

The primary tumor histopathology will be reviewed and will be evaluated with special staining to identify, if possible, the presence or absence of cancer stem cells and niche bodies.

The response of each subject to the intraperitoneal implantation of the RENCA agarose-agarose macrobeads will then be measured over the ensuing 3 months (and a 6, 9, and 12 months, if possible) with respect to changes in:

- Primary tumor size
- Size or number of secondary/metastatic tumors
- Tumor marker or relevant biochemical parameters such as liver enzymes, alkaline phosphatase, lactic dehydrogenase
- Cellular or humoral immune status
- Global clinical status or rating
- Performance status (Karnofsky PS and ECOG PS)
- Activities of daily living (ADL) rating
- Symptom rating/severity (including use of pain medications)
- Quality of life scale
- Circulating tumor cells (when possible)

After each successive implant, follow-up will be at Days 14, 30, 60, and 90. Because much of the testing will be objective in terms of quantifiable clinical laboratory and imaging testing, bias on the part of subjects, investigator, and analysts should be minimized.

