7.1 Determination of Sample Size

Seventy-four (74) male and female subjects with advanced pancreatic or metastatic, treatment-resistant colorectal cancer meeting the protocol inclusion criteria will be sought for this study. Each subject will serve as his/her own control with measurements obtained and evaluated in an unbiased manner. This means that changes from baseline to various post-treatment time points will be analyzed for some variables (such as tumor markers, for example). The confidence intervals for these changes will be calculated. Of course, it is not planned for the survival analysis which will use a retrospective patient population comparison as defined in the Statistical Analysis Plan (a copy of which is attached). The colorectal patient data from this study has already been used to plan a controlled Phase IIb protocol for colorectal cancer. Data from the pancreatic patients, when completed, will be utilized to plan a phase IIb controlled protocol for the pancreatic patients.

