1 ADMINISTRATIVE STRUCTURE

This study is being conducted under the sponsorship of The Rogosin Institute (“the Sponsor”). The clinical monitoring, data management and statistical analyses of safety and efficacy are being performed under contract with Vital Systems, Inc. (VSI), in collaboration with the Sponsor.

This SAP supersedes any statistical considerations identified in the study protocol. Any differences between this statistical analysis plan and the study protocol will be presented and explained in the CSR.

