2 INTRODUCTION

This Statistical Analysis Plan (SAP) describes the statistical analysis methods and data presentations to be used in the summary and analysis of Protocol No. 0911010739, Amendment 10, dated 27 June 2013. Related documents are the study protocol and CRF.

From experiences gained from this and other studies of macrobeads containing mouse renal adenocarcinoma (RENCA) cells, it has become apparent that tumor measurements often cannot be obtained from patients with such advanced disease due to a lack of tolerance to imaging contrast. As a result, certain efficacy parameters (such as response rate) described in the protocol have been modified to better fit the patient population. Therefore this SAP supersedes the statistical considerations identified in the protocol.

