10.2 Statistical Analysis Methods

- All statistical testing will be considered strictly exploratory as the study was not powered based on statistical considerations.
- Exact 95% CIs will be calculated for rates.
- Survival analysis methods will be used analyze time-to-event outcomes; for non-mortality outcomes, the term “survival” will still be used to describe non-occurrence of the event being analyzed. Kaplan-Meier plots with 95% CIs will be generated to show probability of survival as a function of time since implantation. In addition, Kaplan-Meier estimates of the median survival time will be reported.
- The relationship between times from diagnosis of Stage IV disease diagnosis to the primary analysis time of origin and primary analysis time of origin to death will be examined (if feasible) using Cox regression model and Kaplan-Meier curves.
- The relationship between time-to-event outcomes and tumor markers (and other covariates, if feasible) will be assessed using Cox regression. Kaplan-Meier plots will be produced for descriptive assessment.
- Survival comparisons by implantation number will be performed, if feasible.
- Other explorations of efficacy data may be performed (if feasible), such as:
 - Testing for effects of baseline values of tumor markers and presenting stratified descriptive statistics, if deemed appropriate.
 - Plotting chronological subject profiles of specific parameters; i.e., plotting a set of parameters over time on the same graph for a given subject.

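### The protocol promises confidence intervals for tumor-marker changes from baseline, but the superseding SAP gives the continuous change no interval, transformation or rank method

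*SAP*

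**What the plan says.** **Protocol.** Section 4.1 states the design principle: "Each subject will serve as his own control". Section 7.1 explains that "changes from baseline to various post-treatment time points will be analyzed for some variables (such as tumor markers, for example" and adds: "The confidence intervals for these changes will be calculated". Section 4.1 makes the same promise. Neither place gives a confidence level or a method. Survival is expressly left out of this own-control approach. Section 7 speaks in general terms of small-sample methods for non-normal data.

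**SAP.** Section 1 says: "This SAP supersedes any statistical considerations identified in the study protocol". Section 13 repeats this, and both sections leave differences from the protocol to be explained in the study report. Intervals appear in two places. Section 10.1.1 gives 95% intervals for the time-to-death analyses. Section 10.2 gives Kaplan-Meier intervals and says: "Exact 95% CIs will be calculated for rates".

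Continuous marker change is governed by 6.2, 10.1.3 and 11.1.3. Section 6.2 says that, in general, "continuous variables will be summarized by numbers of patients, means, standard deviations, medians and ranges". Section 10.1.3 adds listings, summaries and individual-subject plots, and defines a tumor-marker response as a fall of at least 20% in CEA, CA 19-9 or both. Section 11.1.3 summarises change relative to both the first and the most recent implant.

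The SAP was written for "Protocol No. 0911010739, Amendment 10, dated 27 June 2013". The protocol under review is Amendment 11, of November 2014, and it still carries the promise.

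**The concern.** The trial has no control arm, and both documents say its purpose is to estimate quantities for planning later trials. An estimate serves that purpose only with its precision. Change in CEA and CA 19-9 is a named secondary outcome, and so is change in CA125. A fall in tumor markers is also part of the protocol's response definition for pancreatic cancer. A programmer who follows the SAP will produce no interval for the size of these changes.

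The scale matters as well. On raw units a mean change weights each subject by baseline level. If levels differ widely between subjects, a few of them set the mean, and it can differ in sign from the typical patient's change. If the interval and its scale are chosen after the data are seen, the choice is post hoc.

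**Working it through.** **1. Which quantities get an interval**

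| Quantity | Protocol | SAP |
|---|---|---|
| Time to death | own-control approach excluded | 95% intervals (10.1.1, 10.2) |
| Marker response, fall of at least 20% | no such cut-off | exact 95% interval, as a rate (10.1.3, 10.2) |
| Continuous marker change | intervals promised (4.1, 7.1) | n, mean, SD, median, range (6.2); no interval |

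The gap is the last row.

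**2. The plan's only precision figure.** Appendix 3 of the protocol gives at most 22 points (colorectal) and 31 points (pancreatic). The half-width for a 50% rate is 1.96 × √(0.25/n):
- n = 20: 21.9 points
- n = 10: 31.0 points

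Both figures reproduce. They concern rates; no figure is given for a marker change. For a 50% marker response the exact 95% interval is 18.7-81.3% (n = 10), 27.2-72.8% (n = 20), 32.4-67.6% (n = 34) and 33.8-66.2% (n = 40). SAP 3.2 plans 20 colorectal and 10 pancreatic subjects. Protocol Appendix 3 now has 74, of whom 40 are pancreatic, so 74 − 40 = 34 are colorectal.

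**3. What an interval for change would look like.** The half-width for a mean is t(0.975, n−1)/√n in SD units: 0.72 (n = 10), 0.47 (n = 20), 0.35 (n = 34), 0.32 (n = 40). On the log scale the estimated ratio is multiplied and divided by exp(t × SD/√n). With an assumed log-ratio SD of 0.5-0.8 that factor is 1.43-1.77, 1.26-1.45, 1.19-1.32 and 1.17-1.29 respectively.

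**4. Does the scale matter?** I simulated 20,000 trials per setting. Raw change = B(R − 1), with baseline B and ratio R lognormal and independent. Assumptions: log-baseline SD 1.5-2.0, log-ratio SD 0.6-0.8, and every subject measured.

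*Median ratio 1 (typical patient unchanged)*

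| n | Raw mean above 0 | Raw t-interval covers its own target |
|---|---|---|
| 10 | 62-69% | 60-80% |
| 20 | 65-76% | 64-82% |
| 34 | 70-83% | 68-84% |
| 40 | 71-85% | 68-84% |

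*Median ratio 0.7 (typical patient falls 30%)*

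| n | Raw mean above 0 | Raw median below 0 | Raw t-interval covers | Raw t-interval excludes 0 | Log-ratio interval excludes 1 | Median interval excludes 0 |
|---|---|---|---|---|---|---|
| 10 | 23-35% | 87-93% | 79-99% | 3-9% | 24-39% | 11-19% |
| 20 | 19-36% | 94-99% | 84-98% | 5-16% | 47-72% | 31-52% |
| 34 | 17-36% | 98-100% | 88-97% | 6-23% | 71-92% | 41-68% |
| 40 | 16-36% | 99-100% | 89-98% | 7-25% | 78-96% | 56-81% |

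At n = 34-40 the three largest changes make up 51-68% of the total absolute change. The log-ratio interval covers about 95% throughout, and the order-statistic interval for the median covers 96-98%. With a rise (mean log ratio 0.2, log-ratio SD 0.5-0.8) the raw t-interval covers 62-79% at n = 34-40.

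With less skew (log-baseline SD 1.0, n = 34-40) the effect shrinks. Raw coverage at ratio 1 is 85-89%. For a 30% fall the raw interval excludes 0 in 11-37% of trials and the log-ratio interval excludes 1 in 72-96%.

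**The case against.** Several stronger readings are tempting, and the documents do not support them.

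- **That the markers are summarised by means alone.** SAP 6.2 lists medians and ranges beside the means, and even has a rounding rule for interquartile ranges: "The number of decimal places for means, medians and interquartile ranges will be the same as the original data plus one". Individual plots are planned too. With a 30% fall the planned median has the right sign in 98-100% of trials at n = 34-40.
- **That the own-control comparison has no valid error bars.** The marker response is a within-patient outcome on a relative scale, and the exact-interval rule for rates reaches it. This stands, but it does not close the gap: it covers only CEA and CA 19-9, leaves out CA125, and gives no size of change.
- **That markers are the only within-patient efficacy comparison.** Tumor size, global assessment, daily living, symptoms, quality of life, pain and ECOG are also analysed as changes from baseline.
- **That a raw t-interval is planned and would fail.** The SAP plans none. If one were added, its undercoverage would depend on the setting: marked with no change or a rise, but 88-98% coverage with a 30% fall at n = 34-40. In the latter case the main loss is precision.
- **That a positive raw mean with a median ratio of 1 is an error.** It is a different target. A lognormal ratio with median 1 has mean exp(SD²/2), which is exp(0.18) = 1.20 to exp(0.32) = 1.38 here.

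It is also fair to say that skewness is not documented beyond the protocol's general remark on non-normal data, that these outcomes are secondary, and that every analysis is exploratory. SAP 6.2 speaks of summaries in general, so it does not forbid an interval. Exploratory status excuses the lack of multiplicity control; it does not remove the need for precision in a trial meant for estimation.

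**Conclusion.** The point holds as a gap between the two documents. The protocol promises confidence intervals for changes from baseline and names tumor markers. The controlling SAP specifies intervals only for rates and survival, and gives the continuous change in CEA, CA 19-9 and CA125 no interval, transformation or rank method. That much rests on the text alone.

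The size of the consequence rests on assumptions: lognormal markers, the SDs shown, independence of baseline and ratio, and complete data. Deaths and missed visits will reduce n at later time points. On those assumptions, for a 30% fall at n = 34-40, the log-ratio interval excludes no change in 71-96% of trials against 6-25% on the raw scale, and it keeps 95% coverage. The primary mortality analysis is not affected. This is an inexpensive correction that should be made, not a flaw that undermines the trial.

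**What to change.** In SAP 10.1.3 and 10.2, specify for CEA, CA 19-9 and CA125, by cancer type and time point, one of the following:

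- the geometric mean ratio to baseline, with a 95% t-interval computed on log(post/baseline) and back-transformed; or
- the median change with a distribution-free 95% interval. This needs no distributional assumption, but it excludes no change less often (41-81% against 71-96% in the setting above).

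Keep the raw medians and ranges in the tables. Extend the method to C-reactive protein and cytokines if they prove similarly skewed. Name the baseline for each interval: SAP 6.4.1.2 resets baseline at every implant, while protocol 7.2 uses the pre-first-implant value throughout. State how values below a detection limit enter the ratio, because SAP 6.2 summarises them with the qualifier removed.

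Log-scaled markers in the Cox models, and intervals for the other change variables, are optional. The cost is SAP wording, one derived variable and some extra tables. No new data are needed.

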6.3 Missing Data

For dates, year and month are required. If day is missing, it will be imputed to be the 15th of the month. Otherwise, missing values will not be imputed for descriptive statistics or analyses unless otherwise specified.

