6.4.1.2 Baseline

Individual baselines will be established for each implant. For a given parameter, baseline for each implant will be the last recorded observation prior to the implant.

6.4.1.3 Implant 1 / Study Day 0

The day of the first implant will be designated as Implant 1 / Study Day 0.

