10.1.3 Change in tumor markers and other biochemical parameters

See [Section 11.1.3](#) below for details on laboratory data collection and reporting. Clinical laboratory parameters will include the tumor markers CEA and CA 19-9. A tumor marker response is defined as a $\geq 20\%$ decrease from baseline in one or both of CEA or CA 19-9.

Other biochemical parameters include:

- Serum enzymes and proteins
- Kidney function (creatinine, blood urea nitrogen (BUN))
- C-reactive protein
- Hematology (leukocytes, hemoglobin, differential, platelets, erythrocyte sedimentation rate (ESR))
- Cytokines
- Cellular and humoral immunity status (observed values will be clinically reviewed to determine presence / absence of each antibody, etc.)
- CA125 is included as part of the assessment of inflammatory response to macrobead placement.

Along with listings and summaries, graphical displays of individual subject observed values over time will be produced for tumor markers, CA125, C-reactive protein, and ESR.

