11.1.3 Clinical laboratory evaluations

Hematology, coagulation, serum chemistry, serum pregnancy, urinalysis, immunology, immunophenotyping, and all other laboratory parameters including those listed in [Protocol Section 5.6](#) will be analyzed at multiple laboratory sites and will be delivered via hard-copy reports to the central data processing center (VSI). Laboratory test names and units of measurement will be standardized by VSI. For select parameters, study day, collection lab, date and time collected, normal range, observed value, change from baseline in relationship to both first and most recent implant, out-of-range flag, and Common Terminology Criteria for Adverse Events (CTCAE) v3.0 toxicity grade (if applicable) will be listed. Laboratory observations with Grade 3 or higher toxicity and/or reported as an AE will be listed. For all parameters, study day, date collected, observed value, normal range, and out-of-range flag will be output to a spreadsheet. For select parameters, observed values and changes from baseline (in relationship to both first and most recent implant) will be summarized for each time point at which laboratory data were collected. Separate series of tables will show numbers and percentages of subjects by out-of-range flag and by toxicity grade. Shift tables will be provided that show numbers and percentages of subjects with normal ↔ abnormal shifts based on out-of-range flags and/or toxicity grades from baseline (in relationship to both first and most recent implant) to each subsequent time point at which laboratory data are collected.

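### Dropping the qualifier from laboratory results treats a reporting limit as a measured value, which can create or hide a tumor marker response

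*SAP*

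**What the plan says.** SAP 6.2 (Data Analysis) gives one rule for laboratory results reported with a qualifier, with `<` as its example: they "will be listed with but summarized without the qualifier". `>` is not printed, but the rule is worded for qualifiers in general.

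SAP 10.1.3 brings the tumor markers under that rule: "Clinical laboratory parameters will include the tumor markers CEA and CA 19-9". It defines a marker response as a 20% or greater "decrease from baseline in one or both of CEA or CA 19-9". It sets no minimum baseline value and makes no provision for results beyond a reporting limit.

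Three other rules bear on this:

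- SAP 6.4.1.2: "baseline for each implant will be the last recorded observation prior to the implant", so the denominator of each percent change is a single result.
- SAP 11.1.3: laboratory parameters "will be analyzed at multiple laboratory sites and will be delivered via hard-copy reports to the central data processing center". On harmonisation it says only: "Laboratory test names and units of measurement will be standardized by VSI". Reporting limits are not mentioned.
- SAP 6.3: "missing values will not be imputed for descriptive statistics or analyses unless otherwise specified". This concerns missing values and gives no rule for values known only to lie beyond a limit.

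**The concern.** A result `<L` says that the value lies somewhere below L. Dropping the sign replaces that statement with the value L itself. Means move upward, and percent changes involving the result reflect the laboratory's limit as well as the patient.

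The consequence is sharpest for marker response, because a continuous change is cut at 20%. A limit that differs between two visits can carry a patient across the cut with no change in the patient. A value above an upper limit at baseline can mask a real fall.

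SAP 3.2 says the trial's main purpose is to estimate parameters for planning later trials. Change in CEA and CA 19-9 is a listed secondary efficacy outcome (SAP 3.3.1 and 10), and SAP 10.2 plans Cox models using tumor markers. A distorted estimate would be carried forward into that planning.

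**Working it through.** The documents state no figure that depends on this rule, so there is none to reproduce. The check applies the SAP's rules to examples. All reporting limits below are assumptions.

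**Step 1. Response after dropping the qualifier.** Percent change = 100 x (later - baseline) / baseline; response if -20% or lower.

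| Baseline, then later | Computed change | Under the SAP | What the qualifiers allow |
|---|---|---|---|
| `<2.5`, `<2.0` | (2.0 - 2.5)/2.5 = -20.0% | response | rise or fall |
| `<5`, `<2` | (2 - 5)/5 = -60.0% | response | rise or fall |
| `<2.5`, 1.8 | (1.8 - 2.5)/2.5 = -28.0% | response | rise or fall |
| `<3.0`, `<2.5` | (2.5 - 3.0)/3.0 = -16.7% | no response | rise or fall |
| 3.0, `<2.5` | (2.5 - 3.0)/3.0 = -16.7% | no response | a fall of more than 16.7% |
| `>1,000`, 900 | (900 - 1,000)/1,000 = -10.0% | no response | a fall of more than 10% |
| 50, `<35` | (35 - 50)/50 = -30.0% | response | a fall of more than 30% |

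Two results below the limit count as a response whenever the later limit is at most 0.80 of the baseline limit. In the sixth row, a true baseline of 5,000 would mean (900 - 5,000)/5,000 = -82%.

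**Step 2. When each error can arise.** With one fixed lower limit L, a baseline of `<L` can be followed only by `<L` (computed 0%) or by a measured value of at least L (no computed fall). A false response therefore needs a lower reporting limit at the later visit than at baseline, through another laboratory or another assay. A hidden fall does not: rows five and six can occur with constant limits.

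**Step 3. What one false responder does.** SAP 10.2 plans exact 95% intervals for rates. For 0/n the upper bound is 1 - 0.025^(1/n); for 1/n the bounds are Clopper-Pearson.

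| n | Source | 0/n | 1/n |
|---|---|---|---|
| 20 colorectal | SAP 3.2 | 0% (0 to 16.8%) | 5.0% (0.1 to 24.9%) |
| 10 pancreatic | SAP 3.2 | 0% (0 to 30.8%) | 10.0% (0.3 to 44.5%) |
| 34 colorectal (74 - 40) | Protocol Appendix 3, item 9 | 0% (0 to 10.3%) | 2.9% (0.1 to 15.3%) |
| 40 pancreatic | Protocol Appendix 3, item 9 | 0% (0 to 8.8%) | 2.5% (0.1 to 13.2%) |

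**Step 4. Effect on the mean.** Assume lognormal values with log-scale SD s from 0.8 to 1.5 and a share p below the limit. With z the standard normal quantile of p, the ratio of the computed mean to the true mean is p x exp(s z - s^2/2) + Phi(s - z). For p = 0.5 and s = 0.8 this is 0.5 x 0.726 + 0.788 = 1.151. Over the range of s:

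| Share below the limit | Inflation of the mean |
|---|---|
| 10% | under 1% |
| 30% | 2 to 5% |
| 50% | 10 to 15% |
| 70% | 33 to 40% (largest near s = 1.0) |

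At 70% the computed median is the limit itself, exp(0.524 s) or 1.5 to 2.2 times the true median.

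**The case against.** A false response needs circumstances that the documents do not establish. Protocol section 2 says that most pancreatic patients have raised CA 19-9 at diagnosis, and inclusion criterion 5b admits patients on rising markers, so a marker below the limit at baseline is not the expected case. The trial has one clinical site (Protocol 5.2). The statement that samples "will be analyzed at multiple laboratory sites" covers a list running from hematology to immunophenotyping, and may mean only that different tests go to different laboratories. SAP 6.2 speaks of summaries and does not say how the response flag is derived, and SAP 16.2 names no response table. In the ordinary case, a measured baseline falling below the limit, using the limit understates the fall. Qualified values stay visible in the listings, medians are reported, and everything is exploratory.

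Most of this stands, and it limits the point to what can happen. It does not remove it: the SAP supplies no value other than the stripped one for deriving response, and listings do not correct a summary.

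Two stronger readings are tempting. A reader might infer that changes of laboratory will generate marker responses in this trial; without limits, frequencies or evidence that one patient's marker moves between laboratories, the documents do not support that. A reader might also infer that the reported standard deviations are badly wrong. SAP 6.2 plans no log transformation, and under the lognormal assumption above the original-scale SD is still 90 to 99% of its true value with half the results below the limit.

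**Conclusion.** The concern holds in a limited form. The SAP states a rule that turns a limit into a measurement, applies it to laboratory data that include CEA and CA 19-9, and defines response with no exception. The rule can therefore produce a false response where the reporting limit falls between visits, and can hide a true fall even where limits are constant. For `>` this rests on the general wording of the rule and on such results occurring.

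How often either error would happen cannot be judged from the documents. One false responder raises the upper confidence bound by about 8 percentage points at n = 20 (16.8% to 24.9%) and about 14 at n = 10 (30.8% to 44.5%). The effect on means is negligible if few values are qualified and material only if about half or more are; those shares are assumptions. The affected outcomes are secondary and exploratory. The primary all-cause mortality analysis does not use these data.

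**What to change.** In SAP 6.2, keep the qualifier as a flag in the analysis data, report the number and percentage of qualified values beside each laboratory summary, and make the median the main summary where qualified values occur. The percentage is needed with the median, because a median falling among qualified values is only a limit.

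In SAP 10.1.3, count a marker response only if a fall of at least 20% holds for every value consistent with the qualifiers. Where the qualifiers leave this open, classify the change as not evaluable and report that number beside the rate. Under this rule 50 to `<35` is a response, while `<5` to `<2`, `<2.5` to 1.8 and `>1,000` to 900 are not evaluable.

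The cost is a few sentences in the SAP and a little programming. No new data are needed, since the listings already carry the qualifier. The downside is that a few apparent responses, and some apparent non-responses, become not evaluable.
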